**8. ACCEPTANCE CRITERIA (JUSTIFY IF NOT APPLICABLE)**

The pulse co-oximeter and sensors will be determined to have equivalent performance based on the agreement of their ARMS values.

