**Protocol Test Abstract:**

This study involves evaluating the accuracy of using Masimo’s INVSENSOR00026 Pulse CO-Oximeter and Sensor to measure hemoglobin, as compared to hemoglobin measurements obtained from various lab analyzer(s). The performance of the sensors will be calculated using arithmetic root mean square (ARMS) analysis of the SpHb values and the reference blood values. Blood samples will be collected from healthy volunteers who undergo a hemodilution procedure wherein blood is repeatedly sampled as the concentration of hemoglobin is reduced by administering intravenous fluids to the volunteer in a controlled manner.

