**1. PURPOSE**

The primary objective of this clinical investigation is to evaluate the accuracy of using Masimo’s INVSENSOR00026 Pulse CO-Oximeter and Sensor to measure hemoglobin, as compared to hemoglobin measurements obtained from various lab analyzer(s). Data using the noninvasive devices will be collected from healthy volunteers undergoing a hemodilution procedure.

This is a nonrandomized single arm study wherein all subjects are enrolled into the experimental arm and receive the INVSENSOR00026 Pulse CO-Oximeter and sensor. Hemodilution will be conducted by delivery of intravenous fluids in a controlled manner to reduce the subject’s blood concentration of hemoglobin to obtain noninvasive hemoglobin readings SpHb at various levels. Reference blood samples will be repeatedly collected from the subject and analyzed using a standard laboratory hematology analyzer. The performance of the sensors will be calculated using arithmetic root mean square (ARMS) analysis of the SpHb values and the reference blood values.

Outcome Measure: Performance of INVSENSOR00026 by ARMS calculation

Performance of the Pulse CO-Oximeter and sensors will be determined by comparing the noninvasive hemoglobin measurement (SpHb) of INVSENSOR00026 to the hemoglobin value obtained from a reference blood sample and calculating the ARMS value.

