6. EQUIPMENT AND MATERIALS

Equipment and Materials: All lab analyzers and equipment will be maintained per manufacturer specifications and all study personnel will be trained on the use of relevant equipment. Equivalent equipment and materials to those listed below may be used.

Safety Equipment (FDA-Cleared)

- Blood pressure monitoring system
- A-line pressure transducer
- Electrocardiogram (ECG)
- Masimo Pulse Oximeters (Radical-7) - for subject safety monitoring
- Pulse oximeter sensors and cables (Masimo SET, Masimo rainbow)
- Masimo Patient Monitoring Platform (Root®)- for subject safety monitoring
- Medical-grade Oxygen tank and mask
- Crash cart

Test Devices

- Masimo INVSENSOR00026 pulse co-oximeter and sensor – Investigational

Research Equipment

- Laboratory co-oximeters/blood analyzers
- Laboratory hematology analyzers

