7. PROCEDURE

7.1. SCHEDULE OF ACTIVITIES

Procedures	Phone Pre-Screen	Baseline Visit 1	Procedure Visit 1
Brief Study Procedure Description	X		
Informed consent		X	
Demographics (including skin tone)	X	X	
Medical history (subject-reported)	X	X	
Concomitant medication review	X	X	
Vital Signs (ECG, Blood Pressure Cuff, Pulse Ox)		X	X
Height	X	X	
Weight	X	X	
ASA Status Assessment		X	
Pregnancy test 		X	
Allen’s Test		X	
Venous sample (via needle stick or IV placement)		X	

Procedures	Phone Pre-Screen	Baseline Visit 1	Procedure Visit 1
Local anesthetics (lidocaine, ethyl chloride spray, or pain ease skin refrigerant) as needed 		X	X
Peripheral Venous Line (IV) 		X	X
Intra-arterial catheter (A-line)			X
Placement of test and control sensors			X
Noninvasive data collection			X
Removal of Blood (if necessary)			X
IV Fluid Administration			X
Continuous A-line sampling			X
Line Removal			X
Post Care Instructions Given		X	X
Discharge		X	X
Adverse Event Review and Evaluation 		X	X

1 hCG (urine) pregnancy test (all female subjects)

2 IV may be placed during screening/baseline to obtain qualifying venous sample at discretion of medical staff. If the IV is placed during screening/baseline, medical staff will offer to use local anesthetics.

3 Adverse events may be reported by the subject after their visit. See section 10 for additional details.

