9.2. Statistical Analysis

Accuracy will be reported as the root mean squared error (ARMS) of the SpHb-tHb parameter. Per ISO 80601 Part 2-61, accuracy of existing pulse oximetry instruments will be reported using ARMS standard calculations which are also applicable to SpHb testing.

$$Bias = \frac{1}{n} \sum_{i=1}^n (SpHb - tHb)$$

$$A_{RMS} = \sqrt{\frac{\sum_{i=1}^n (SpHb - tHb)^2}{n}}$$

9.3. Measures taken to minimize/avoid bias:

- 9.3.1. Sensors and devices will be provided to operators in a way that minimizes the operator bias. Sensors and devices will be provided at random when deemed necessary.
- 9.3.2. Operators will not make any decisions based on results from other operators or any parameters obtained from blood samples.

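### The visible acceptance rule in section 8 concludes equivalence from agreement of unidentified ARMS values, with no margin and no upper limit on ARMS, in a single-arm accuracy study

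*Combined protocol and SAP*

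**What the plan says.** Section 8 of the combined protocol and SAP, the acceptance criteria, consists of one sentence: "The pulse co-oximeter and sensors will be determined to have equivalent performance based on the agreement of their ARMS values". It carries no redaction mark and refers to no other section or document. It is the only pass/fail rule that can be seen.

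The other sections describe a different question:

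- **Abstract:** "The performance of the sensors will be calculated using arithmetic root mean square (ARMS) analysis of the SpHb values and the reference blood values".
- **Section 1, design:** "This is a nonrandomized single arm study wherein all subjects are enrolled into the experimental arm".
- **Section 1, outcome:** performance is to be found by "comparing the noninvasive hemoglobin measurement (SpHb) of INVSENSOR00026 to the hemoglobin value obtained from a reference blood sample" and calculating ARMS.
- **Section 9.2:** "Accuracy will be reported as the root mean squared error (ARMS) of the SpHb-tHb parameter". Formulas follow for bias and ARMS of SpHb minus tHb. No limit, margin, interval or between-device comparison is given.

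On possible comparators, the test-device list in section 6 has a single entry, "Masimo INVSENSOR00026 pulse co-oximeter and sensor". The other Masimo oximeter in that section is there for safety monitoring. The schedule in section 7.1 has a row for "Placement of test and control sensors", but no control sensor is identified anywhere or given a role in the analysis. Section 2.2 names two cleared predecessors, Rad-57 and Pronto, as background and gives no ARMS for either.

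**The concern.** The objective is accuracy against a laboratory reference. The acceptance rule concludes equivalence to something unnamed. The metric is the same in both places, but the conclusion is not.

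Three things needed to apply the rule are missing from it: whose ARMS values are compared, what difference counts as agreement, and what ARMS is acceptable. Followed to the letter, it could declare success when both ARMS values are large. It could also deny success to a device that is more accurate than its comparator. With no number fixed in advance, what counts as agreement could be settled after the data are seen.

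**Working it through.** The plan gives no figure to reproduce: the sample size in section 9.1 is redacted, and no SD, margin, ARMS limit, alpha or power is visible. The check therefore reads the sentence against the rest of the plan and then works through the arithmetic of ARMS. All g/dL values below are assumed for illustration.

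**Step 1. What could *their* refer to?**

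- *Oximeter versus sensor.* This is the literal grammar. Section 2.2 describes the two as one system, and section 9.2 defines one ARMS for it, so there is nothing for that value to agree with.
- *Test versus control sensor.* Section 7.1 allows this reading. A within-subject comparison is possible in a single-arm study, but the control is not identified and section 9.2 has no such analysis.
- *One unit versus another of the same model.* Possible, but not stated.
- *INVSENSOR00026 versus a cleared predecessor.* Section 2.2 suggests this. If the predecessor's ARMS were known and small, agreement with it would act as an indirect ceiling. No such ARMS is given, and nothing confirms this reading.

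**Step 2. Agreement of ARMS does not show accuracy.** From the formulas in section 9.2, with SD computed with divisor n:

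ARMS² = bias² + SD²

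- Sensor A, bias +2.4, SD 1.8: √(5.76 + 3.24) = √9.00 = 3.0 g/dL.
- Sensor B, bias -2.4, SD 1.8: √(5.76 + 3.24) = 3.0 g/dL.

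The difference in ARMS is 0, so agreement is perfect. Yet both sensors are far from the reference, and their mean readings are 2.4 + 2.4 = 4.8 g/dL apart.

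**Step 3. Disagreement of ARMS does not show inaccuracy.**

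- Test sensor, bias 0.3, SD 0.8: √(0.09 + 0.64) = √0.73 = 0.85 g/dL.
- Comparator, bias 1.2, SD 0.9: √(1.44 + 0.81) = √2.25 = 1.50 g/dL.

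The difference is 1.50 - 0.85 = 0.65 g/dL, and the test sensor is the better one.

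**Step 4. The conclusion turns on the missing margin.** Simulation with assumed true ARMS of 1.0 and 1.3 g/dL, 10 pairs per subject, within-subject correlation 0.5, zero bias, independent errors for the two devices, 4,000 runs. Share of studies in which the two observed ARMS values fall within the margin:

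| Subjects | 0.1 g/dL | 0.25 g/dL | 0.5 g/dL |
|---|---|---|---|
| 10 | 13% | 42% | 85% |
| 20 | 8% | 37% | 92% |
| 40 | 3% | 32% | 97% |

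The same pair of devices would usually fail at one plausible margin and usually pass at another.

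**The case against.** The strongest reply is that the study still delivers what section 1 asks for. The objective is to evaluate accuracy, the outcome is ARMS, and section 9.2 reports exactly that. Every ARMS in the plan is by definition error against tHb. This stands: the objective, the outcome and the estimator are sound, and only the acceptance conclusion fails.

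Second, if agreement means agreement with a cleared predecessor of established accuracy, the example with both values at 3.0 g/dL loses most of its force. Section 9.2 also mentions that accuracy of existing oximetry instruments is reported as ARMS. That sentence reads most naturally as support for the choice of metric. The predecessor reading narrows the concern but does not remove it, because no predecessor is named as comparator and neither its ARMS nor a margin is given.

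Third, a limit may exist where it cannot be seen: section 3, parts of section 7.4, and the sample size and procedure reference in section 9.1 are redacted. A reader might infer that the study had no accuracy limit at all. The documents do not support that. They show only that section 8 states none and points to none; the internal procedures cited in section 9.1 are cited for sample size. Even if a limit exists elsewhere, section 8 has to be reconciled with it.

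A reader might also infer that the device is inaccurate. Nothing here bears on that; the values in the working are assumed.

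**Conclusion.** The concern holds for the acceptance conclusion and no further. As worded, the section 8 sentence cannot be applied, and it points to a conclusion, equivalence, that the visible plan is not set up to test. Because it is the only visible decision rule, it should be corrected before any acceptance conclusion is drawn from it.

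The documents allow no numerical size: they do not say which of the cases in the working, if either, applies. The text finding rests on no assumption beyond reading the visible sentence as complete. The illustrations rest on assumed biases, SDs, numbers of subjects and correlations.

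**What to change.** **Section 8.** Replace the sentence with an absolute criterion: *INVSENSOR00026 meets the acceptance criterion if ARMS of SpHb minus tHb is at or below X g/dL.* State X, or cite the existing internal limit, and fix it before the first subject. The documents supply no value for X, so none is proposed here.

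**Section 9.2.** Report with ARMS a one-sided 95% upper bound that allows for repeated samples within subject, for example a generalized confidence bound for bias² plus between-subject plus within-subject variance. Making that bound the pass criterion is optional.

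**Only if device equivalence is truly intended.** Name the comparator in section 6, state a margin, and add to section 9.2 a paired comparison on the same draws that allows for clustering by subject. This comes in addition to the absolute limit, and it is a further analysis to be planned and sized.

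**Cost.** The minimum change is one reworded sentence and one added calculation, but an explicit limit can be failed. The table evaluates the fix and is not evidence of the defect. It is illustrative, on assumed inputs: 15 to 30 subjects, 20 pairs each, zero bias, normal errors, 8,000 runs per cell. ICC is the between-subject share of error variance, and each range runs over the number of subjects.

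| Criterion | True ARMS relative to X | ICC 0.2 | ICC 0.5 | ICC 0.8 |
|---|---|---|---|---|
| Estimate at or below X | 80% of X | about 100% | 99–100% | 95–99% |
| Estimate at or below X | 10% above X | 1–4% | 9–19% | 20–29% |
| Bound at or below X | 80% of X | 83–100% | 39–77% | 22–49% |
| Bound at or below X | 10% above X | about 1% or less | about 1% or less | about 1% or less |

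A device exactly at X passes 52–55% of the time on the estimate and 2–3% on the bound. The estimate is easy on a good device but lenient near the limit; the bound is strict and costs power when errors cluster by subject. With heavier-tailed errors (t, 5 df), the bound passes a device at the limit 7–11% of the time, above the nominal 5%. The sponsor should check the chance of passing at the redacted sample size before choosing between the two.

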**9. SAMPLE SIZE JUSTIFICATION AND DATA ANALYSIS PROCEDURE TO BE USED**

9.1. Sample size determination

Sample size for this study has been determined to be [REDACTED] based on previous experience with similar devices and Masimo internal procedures for sample size calculation and justification ([REDACTED]).

9.2. Statistical Analysis

Accuracy will be reported as the root mean squared error (ARMS) of the SpHb-tHb parameter. Per ISO 80601 Part 2-61, accuracy of existing pulse oximetry instruments will be reported using ARMS standard calculations which are also applicable to SpHb testing.

$$Bias = \frac{1}{n} \sum_{i=1}^n (SpHb - tHb)$$

$$A_{RMS} = \sqrt{\frac{\sum_{i=1}^n (SpHb - tHb)^2}{n}}$$

9.3. Measures taken to minimize/avoid bias:

- 9.3.1. Sensors and devices will be provided to operators in a way that minimizes the operator bias. Sensors and devices will be provided at random when deemed necessary.
- 9.3.2. Operators will not make any decisions based on results from other operators or any parameters obtained from blood samples.

9.4. Expected drop out rates

Subjects may not complete the study for various reasons, such as screen failure, unable to complete hemodilution criteria, unable to have intravenous or arterial line placed. [REDACTED]

**10. ADVERSE EVENTS**

Definitions:

Adverse event: Any untoward medical occurrence in a subjects, users or other persons, whether or not related to the medical device under study.

Device-related adverse event: Adverse event related to, associated with, or caused by, the use of a medical device under study, including but not limited to events that may have been attributed to the device because of device failure or malfunction, improper or inadequate design, manufacture or user error.

Device deficiency: Inadequacy of a medical device with respect to its identity, quality, durability, reliability, safety or performance. Device deficiencies include malfunctions, use errors and inadequate labeling.

Serious adverse event: Adverse event that: a) led to death, b) led to serious deterioration in the health of the subject, that resulted in: (i) a life-threatening illness or injury, (ii) a persistent or significant impairment of a body structure or a body function, (iii) in-patient or prolonged hospitalization, or (iv) medical or surgical intervention to prevent life-threatening illness or injury or permanent impairment to a body structure or a body function, or c) led to fetal distress, fetal death or a congenital abnormality or birth defect. NOTE: Planned hospitalization for a pre-existing condition, or a procedure required by the clinical investigational plan, without serious deterioration in health, is not considered a serious adverse event.

All adverse events will be reported and documented as described below.

#### 10.1. Adverse Events

All adverse events that occur during the study shall be recorded on the Case Report Form even if the investigator assesses the adverse event as unlikely to be causally related to the test device or study procedures. The investigator will inform the sponsor and IRB as required by IRB reporting guidelines.

#### 10.2. Serious Adverse Events

10.2.1 The investigator/study staff shall promptly report both serious adverse events (e.g., subject death, subject hospitalization for several days) and unanticipated adverse device effects to the sponsor within 48 hours. All serious adverse events will also be reported to the IRB per IRB reporting requirements.

10.2.2 At the time of discharge from the study, any unresolved serious adverse event(s) will be followed up by the investigator until the event(s) are resolved, stabilized or the patient is lost to follow-up or the adverse event is otherwise explained. The investigator will also instruct the subject to report any subsequent events occurring in the next 30 days, which the subject or the subject's physician believes might reasonably be regarded as caused by or have a reasonable possibility of being caused by the test device or procedures involved in the study.

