- 13.6. Blood Draw risks: discomfort is generally associated with needle puncture. The most common complications associated with blood draws and capillary sticks are hematomas or bruising. All blood draws will be performed by qualified personnel. An ACLS certified physician will be in attendance throughout the entire procedure, and the study will be completed under their general supervision. Other anticipated adverse events that may occur, include but are not limited to: Vaso vagal (passing out), infiltrated IV, lightheadedness, feeling flush/ warm, feeling nauseated, throwing up, seizures, sudden drop in blood pressure/ sudden increase in blood pressure, sudden drop in heart rate/ sudden increase in heart rate, tingling sensation of face/arms and/or sweating, and mouth dryness. These anticipated adverse events are expected to be temporary.
- 13.7. Risk From Hemodilution: Hemodilution has been used successfully as a technique to reduce perioperative blood loss during surgery. Hemodilution is generally considered to be safe in most patients and exceptionally safe in healthy volunteers. In surgery, the chief benefit of hemodilution is the reduction of blood losses when whole blood is shed perioperatively at lower hematocrit levels after hemodilution is completed. In our controlled clinical lab, withdrawal and blood loss will be limited to samples required for laboratory analysis; hemodilution will be used principally to lower the subject's hematocrit and hemoglobin. The risks of hemodilution include heart failure, respiratory failure, hypertension, edema, infection and electrolyte abnormalities. Isotonic fluids will

be administered. A physician will be immediately available thorough out the procedure and vital signs will be continually monitored.

13.8. Risk from Inflicted Knowledge: The risk of inflicted medical knowledge to volunteers is negligible since we deidentify all associated sample information including those relevant to our clinical and engineering parameter studies. The monitoring and test results are not examined for diagnostic purposes and do not reflect an attempt to ascertain any subject's medical condition. The attending physician's role during this study is to ensure the safety of the subject during the study. Subjects are informed that these are not diagnostic tools, if observations are made using FDA cleared devices we will refer them to their primary care physician.

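### After discharge, 10.2.2 puts the subject's or physician's view of possible relatedness ahead of the investigator's, with no scheduled contact to catch what this leaves out

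*Combined protocol and SAP*

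**What the plan says.** Section 10 defines an adverse event as an untoward medical occurrence "whether or not related to the medical device under study". Section 10.1 sends every adverse event during the study to the Case Report Form "even if the investigator assesses the adverse event as unlikely to be causally related to the test device or study procedures". Section 10.2.1 requires serious adverse events to reach the sponsor within 48 hours and attaches no relatedness condition to them.

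Section 10.2.2 deals with the time after discharge and has two parts. For events already open it is unconditional: "At the time of discharge from the study, any unresolved serious adverse event(s) will be followed up by the investigator until the event(s) are resolved", or until another stated end point such as stabilization or loss to follow-up. For new events, the investigator will "instruct the subject to report any subsequent events occurring in the next 30 days", limited to those that either the subject or a physician caring for them "believes might reasonably be regarded as caused by or have a reasonable possibility of being caused by the test device or procedures involved in" this trial. The sentence stands under the serious adverse event heading but speaks of subsequent events generally.

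Two other places bear on the same period. Footnote 3 to the schedule in 7.1 says that subjects may report adverse events after the visit and refers to section 10 for details. Section 7.4.17 tells volunteers to contact the principal investigator about any possible complication. The schedule marks adverse event review at Baseline Visit 1 and Procedure Visit 1 and at no later time.

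**The concern.** Up to discharge, the investigator sees every event and then judges its cause. After discharge the order is reversed for new events: someone outside the study team decides whether a link is possible, and the investigator hears of the event if that person thinks so. With no scheduled contact, nothing in the visible plan picks up what this step leaves out.

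The protocol's own risk list suggests why this could matter. Section 13.7 states: "The risks of hemodilution include heart failure, respiratory failure, hypertension, edema, infection and electrolyte abnormalities". Section 13.4 adds infection, nerve damage and loss of feeling after arterial cannulation. Some of these could plausibly first show at home, and a subject might put them down to something else. An effect that nobody warned about is the one a subject is least likely to connect with the study. At stake is the completeness of safety information from an invasive procedure in healthy volunteers.

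**Working it through.** The protocol gives no figure on this point, so the check is a comparison of its rules.

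| Place | Period covered | Relatedness condition before the investigator hears of it |
|---|---|---|
| Section 10, definition | not limited | none |
| 10.1 | during the study | none |
| 10.2.1 | not limited (serious events) | none for serious adverse events |
| 10.2.2, open serious events | after discharge | none |
| 10.2.2, new events | 30 days after discharge | possible relatedness, in the view of the subject or the subject's physician |
| 7.1, footnote 3 | after the visit | none stated, but permissive and refers back to section 10 |
| 7.4.17 | not limited | none stated, but the event must look like a complication |

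**Trace one event.** Suppose a subject is hospitalized on day 10, and neither the subject nor the treating physician thinks of the study.

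1. 10.2.2 does not ask the subject to report it.
2. Footnote 3 allows a report but does not ask for one, and it points back to section 10.
3. 7.4.17 asks for a call only if the subject sees the event as a possible complication. It follows the wound-care instruction, and the word complication itself suggests a link to the procedure.
4. No contact is scheduled at which staff would ask.
5. Unless the site learns of it in some other way, the investigator cannot assess relatedness, and the 48-hour report under 10.2.1 is not triggered.

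The same hospitalization during the study would be recorded under 10.1 and reported under 10.2.1 whatever its cause.

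**Size.** An estimate needs the number of subjects N (redacted in 9.1), the rate p of delayed related events (not given) and the share r of them that the subject or physician recognizes as possibly related (not given). It therefore cannot be computed. Purely as an illustration, assume N = 30 and p = 5%. The chance that the investigator learns of at least one such event is 1 − (1 − p·r)^N:

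- r = 1: 1 − 0.95^30 = 0.785, or 79%
- r = 0.5: 1 − 0.975^30 = 0.532, or 53%
- r = 0.3: 1 − 0.985^30 = 0.365, or 36%

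None of these inputs comes from the protocol. The r = 1 line needs every event to be reported, which self-report would not guarantee even under better wording, and the calculation gives no credit to footnote 3 or 7.4.17. It shows the direction of the effect, not its size in this trial.

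**The case against.** A good deal can be said for the text as it stands.

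- **The periods differ.** A reader might infer that 10.2.2 contradicts 10.1. It does not: 10.1 covers events during the study and 10.2.2 covers events after discharge from it, so both can be followed. What remains is that the standard changes at discharge, and that the protocol does not say whether the 30 days count as part of the study.
- **The threshold is low.** A reader might infer that an event is reported only if someone already believes the study caused it. The text asks for possible relatedness, and either the subject or the physician can meet that. This stands, but it does not help with an event that neither of them links to the study at all.
- **There are other routes.** Footnote 3 and 7.4.17 state no belief in causation, so 10.2.2 is not the only path. They narrow the gap without closing it, for the reasons traced above.
- **Subjects are told the risks.** Section 5.1 requires that they understand them, and 7.3.1 gives time to read and ask. The consent form and the text of the post-care instructions are not available here, so nothing can be concluded about what they say. Section 5.1 does not speak to the subject's own physician.
- **Delayed onset is not documented.** Section 13.7 gives no timing for the listed risks. That some may appear after discharge is an inference, though the sponsor's own 30-day window suggests that later events are thought worth hearing about.
- **No safety analysis is affected.** The only stated outcome is ARMS, and no adverse event rate or pooled count is planned. This is correct and limits the weight of the point.

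**Conclusion.** The point holds as a minor one. For new events after discharge, the protocol places a non-investigator's view of possible relatedness ahead of reporting, schedules no contact to compensate, and so applies a narrower standard than its own definition, 10.1 and 10.2.1. A delayed event may be missed when neither the subject nor the physician makes the connection.

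A reader might go further and conclude that delayed harm will be undercounted, or take the illustrative percentages as an estimate. The documents support neither: they show that events could be missed, not that they will be or how many. The conclusion assumes that 10.2.2 is the governing rule for new events in the 30 days and that the post-care instruction, which cannot be seen here, does not already ask for all events. The ARMS accuracy conclusion does not depend on any of this. It is best treated as a cheap improvement to safety ascertainment.

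**What to change.** 1. Reword the second sentence of 10.2.2 so that subjects are told to report any new medical event, medical visit or hospitalization in the 30 days after discharge, whatever they or their physician think caused it. The investigator then assesses relatedness and seriousness.
2. State that recording under 10.1 and reporting under 10.2.1 apply through those 30 days.
3. Bring footnote 3 in 7.1, section 7.4.17 and the post-care instruction into line with the new sentence.

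The cost is one sentence, one clarification and matching edits, plus a few unrelated events on the Case Report Form. The change removes the relatedness filter. It still relies on subjects to call, so it does not by itself ensure complete reporting.
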